	 Patients who, in the opinion of the investigator, are not able to comply with study treatment or who have any medical or mental disorder, situation, or diagnosis, which could interfere with the proper completion of the study protocol requirements or pose a safety risk while participating in the study. Parent/guardian has a history of psychiatric disease, intellectual deficiency, substance abuse, or other condition (e.g. inability to read, comprehend and write) which will limit the validity of consent for their child to participate in this study. Hemoglobin levels outside normal ranges at screening. Any surgical or medical condition which might significantly alter the absorption, distribution, metabolism, or excretion of drugs, or which may jeopardize the patient in case of participation in the study. Patients who have a clinically significant ECG abnormality or clinically significant abnormal lab values reported at Screening Visit. Patients with a history of long QT syndrome or whose corrected QT interval (QTc) measured at Screening Visit (Fridericia method) is prolonged (≥ 450 msec for males and females 6 - 12 years old). Use of any prescription drugs, herbal supplements, prescribed medicinal use of cannabis/marijuana, within four weeks prior to initial dosing, and/or over-the-counter (OTC) medication, dietary supplements within two weeks prior to initial dosing. If needed, (i.e. an incidental and limited need) paracetamol/acetaminophen is acceptable, but must be documented in the Concomitant medications / Significant non-drug therapies page of the CRF. History of malignancy of any organ system, treated or untreated, within the past 5 years, regardless of whether there is evidence of local recurrence or metastases. Patient is an immediate family member of the participating investigator, sub-investigator's discretion). Inability to properly train in the use of the In-Check DIAL[®] at
	 23. Patients receiving any medications in the classes specified in Table 6-2 unless they undergo the required washout period prior to Day 1. 24. Patients who are sexually active.
Study treatment	Treatment A: MF Twisthaler [®] 100 µg
	Treatment B: QMF149 Concept 1 Breezhaler [®] (indacaterol acetate 75 µg/MF
	40 µg)
Efficacy assessments	None
Pharmacodynamic assessments	None

Pharmacokinetic assessments	The following parameters will be calculated for MF AUC0-6h Cmax Tmax AUCinf Lambda_z T1/2 CL/F Vz/F 	

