4.1 Rationale for study design

This is an open-label, two-period, single-sequence, crossover study in 24 asthma patients aged ≥ 6 to <12 years. The trial is designed to compare the systemic exposure of single inhaled doses of mometasone furoate (MF) when administered alone as MF TH 100 µg or as an indacaterol acetate/MF fixed dose combination (QMF149 75/40 µg) via the Concept 1 (C1) device.

Blood samples for assessment of MF concentrations will be collected from pre-dose to 6 hours after each dose of MF TH or QMF149 C1. Based on data in CQMF149E2101, blood collection up to 6 hours is considered adequate since the MF PK parameter AUC0-6h is projected to be

approximately 40-50% of AUC0-24h after single inhalation dose of MF TH or QMF149 Concept 1. This provides reasonable data for comparison of the two formulations. Since the Tmax of MF is approximately 1h post inhalation dose of MF TH or QMF149 C1, the planned PK sampling schedule allows reliable assessment of Cmax for comparative assessment of both formulations.

Confidential

Single-dose assessment is preferred as it is a more sensitive marker to measure bioavailability. The crossover study design is favored to assess relative bioavailability between two formulations as each patient serves as his/her own matched control, thereby requiring fewer patients to attain the same level of statistical power or precision as a parallel design. Single-sequence crossover design including administration of MF TH in the first treatment period followed by QMF149 administration in the second treatment period enables a shorter washout duration of 4 days based on MF T1/2 (mean: 12-13 hr) following MF administration via TH or C1 in adult healthy volunteers.

This study planned in ≥ 6 to < 12 years old pediatric asthma patients will confirm the comaparability of mometasome exposure between two formulations and support the QMF149 pediatric development program. Due to ethical considerations, healthy volunteers in this pediatric age group are not being considered. A study in adult healthy volunteers was not considered due to the difficulty in extrapolation of PK data of inhaled therapies from adults to pediatric patients resulting from differences in inhalation pattern, lung and airway geometry, and surface area between both age groups.

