8.5.1 Pharmacokinetics

PK samples will be collected at the visits defined in the assessment schedule. Follow instructions outlined in the laboratory manual regarding sample collection, numbering, processing and shipment. Residual samples will be retained for additional PK analysis if necessary.

The number of samples/blood draws and total blood volume collected will not exceed those stated in the protocol. Pharmacokinetic (PK) samples will be obtained and evaluated in all patients at all dose levels.

Mometasone furoate and indacaterol will be determined by a validated LC-MS/MS method; the anticipated Lower Limit of Quantification (LLOQ) is 0.25 pg/mL for mometasone and 5.0 pg/mL for indacaterol. Concentrations will be expressed in mass per volume units and will refer to the free base. Concentrations below the LLOQ will be reported as "zero" and missing data will be labeled as such in the Bioanalytical Data Report.

Blood collection (Table 16-4):

- 2 mL blood per sample, EDTA tubes (plasma): Day 1 and Day 6: pre-dose, 0.5, 1, 2, 3, and 6h post-dose for MF analysis
- 1 mL blood per sample, Lithium Heparin tubes (plasma): Day 6 pre-dose, 0.25 and 1 h post-dose for IND analysis

Analytes, media and methods: Determination of mometasone furoate in plasma will be performed by a validated LC-MS/MS method with an LLOQ at 0.25 pg/mL for mometasone furoate and 5 pg/mL for indacaterol.

The following pharmacokinetic parameters will be determined using the actual recorded sampling times and non-compartmental method(s) with Phoenix WinNonlin (Version 6.4 or higher): Cmax, Tmax, AUC0-6h from the MF plasma concentration-time data.

To maintain the consistency for any potential effect of food on the PK profile of mometasone, all patients are encouraged to consume a snack approximately 1 hour post-dosing and a meal approximately 4 hours post-dosing.

Due to a drug substance coating effect on inner plastic surfaces of the inhaler, the first delivered dose and Fine Particle Mass (FPM) from fresh C1 Breezhaler[®] device delivered dose and fine particle mass is known to be generally slightly lower compared to the average delivered doses.

For comparison purpose of MF delivered in QMF149 through C1 Breezhaler[®] and MF delivered by Twisthaler[®] the blood exposure values (e.g., Cmax, AUC0-6h) obtained with C1 Breezhaler[®] will be multiplied with the factor FPM_{primed} (MF) / $FPM_{unprimed}$ (MF) to assess equivalent MF component doses.

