# 2.5.2 Statistical hypothesis, model, and method of analysis

Log-transformed PK parameters Cmax and AUC(0-6h) will be analyzed for mometasone furoate by linear fixed effects model with treatment and patient as fixed effect. The estimated mean and 90% confidence interval of treatment difference of test vs reference (QMF149 vs MF) will be back transformed to obtain the geometric mean and 90% confidence intervals (CI) of the ratio.

Indacaterol and mometasone furoate plasma concentration data will be listed by treatment, patient, and visit/sampling time point. Descriptive summary statistics will be provided by treatment and visit/sampling time point, including the frequency (n, %) of concentrations below the LLOQ and reported as zero.

Summary statistics will include mean (arithmetic and geometric), standard deviation (SD), Coefficient of Variation (CV) (arithmetic and geometric), median, minimum, and maximum.

Novartis	Confidential	Page 12 of 16
SAP Amendment 1		Study No. CQMF149G2203

Indacaterol and mometasone furoate pharmacokinetic parameters will be listed by treatment and patient. Descriptive summary statistics will include mean (arithmetic and geometric), SD, and CV (arithmetic and geometric), median, minimum, and maximum. An exception to this is Tmax where median, minimum, and maximum will be presented. PK parameters AUC0-6h and Cmax will be used for comparison of MF exposure after the two treatments.

Arithmetic mean (+/- SD) and overlaying individual plots for plasma concentration data will be presented by treatment and also by age group.

For comparison purpose of MF delivered in QMF149 through C1 Breezhaler® and MF delivered by Twisthaler® the blood exposure values (e.g., Cmax, AUC0-6h) obtained with C1 Breezhaler® will be multiplied with the factor FPMprimed (MF) / FPMunprimed (MF) to assess equivalent MF component doses.

For MF Twisthaler, the correction factor is 1.26, for MF Concept 1 device the correction factor is 1.62 and for Indacaterol Concept 1 device the correction factor is 2.0.

Similar analysis as mentioned above will be performed using a correction factor for plasma PK concentration and PK parameters.

The following pharmacokinetic parameters (Table 2-1) will be determined using the actual recorded sampling times and non-compartmental method(s) with Phoenix WinNonlin (Version 8.0 or higher):

AUC0-6h	The AUC from time zero to the last sampling time point 6h (mass x time x volume- 1)

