AUCinf	The AUC from time zero to infinity (mass x time x volume-1)
AUClast	The AUC from dosing to the time of the last measured concentration.
Cmax	The maximum (peak) observed plasma drug concentration after single dose administration (mass x volume-1)
Tmax	The time to reach maximum (peak) plasma, or other body fluid drug concentration after single dose administration (time)
Lambda_z	Smallest (slowest) disposition (hybrid) rate constant (time-1) may also be used for terminal elimination rate constant (time-1)
T1/2	The elimination half-life associated with the terminal slope ( $\lambda z$ ) of a semi logarithmic concentration-time curve (time). Use qualifier for other half-lives
CL/F	The total body clearance of drug from the plasma (volume x time-1)
Vz/F	The apparent volume of distribution during terminal phase (associated with $\lambda z$ ) volume.

 Table 2-1
 Non-compartmental pharmacokinetic parameters

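### MF half-life, lambda_z, CL/F, Vz/F and AUCinf are to be derived from samples ending at 6 h, which cannot show the terminal phase; T1/2 would be biased low by an undetermined amount

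*SAP*

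**What the plan says.** **Commitment to derive the parameters.** SAP 2.5.2 reads "The following pharmacokinetic parameters (Table 2-1) will be determined using the actual recorded sampling times and non-compartmental method(s". Table 2-1 then lists AUC0-6h, AUCinf, AUClast, Cmax, Tmax, lambda_z, T1/2, CL/F and Vz/F. It defines lambda_z as the slowest rate constant and T1/2 as "The elimination half-life associated with the terminal slope". The SAP sentence names no analyte. The protocol summary does: "The following parameters will be calculated for MF", followed by a list that includes AUCinf, lambda_z, T1/2, CL/F and Vz/F.

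**Other statements in the protocol.** Section 8.5.1 commits only to "Cmax, Tmax, AUC0-6h from the MF plasma concentration-time data". Section 12.5.2 treats half-life as optional and qualitative, although its Table 12-1 defines the full set. SAP Section 4 declares no departure from the protocol.

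**Sampling and kinetics.** MF is sampled on "Day 1 and Day 6: pre-dose, 0.5, 1, 2, 3, and 6h post-dose for MF analysis". Protocol 4.1 gives a Tmax of about 1 h and bases the washout on a half-life from an adult study: "based on MF T1/2 (mean: 12-13 hr) following MF administration via TH or C1 in adult healthy volunteers". The same section projects AUC0-6h as "approximately 40-50% of AUC0-24h after single inhalation dose of MF TH or QMF149". It defends 6 h sampling as adequate for comparing the two formulations and makes no claim that it supports a terminal slope.

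**Exclusion rule.** SAP 2.5.3 and protocol 12.4.3 exclude from the primary analysis any patient with a missing PK parameter in one period. Both give AUCinf as an example.

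**The concern.** With Tmax near 1 h, the samples clearly after the peak are those at 2, 3 and 6 h. A slope through them describes a terminal phase only if that phase has begun by 2 h, and the protocol's own projection suggests it has not. Neither document states when a lambda_z estimate is acceptable: there is no minimum number of points, fit criterion or limit on extrapolation.

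At stake are descriptive values. The report would tabulate a terminal half-life and clearance for children that reflect where sampling stopped, and a reader comparing them with the adult 12-13 h could not tell a paediatric difference from an artefact. There is also one textual link to the primary analysis: the exclusion rule names AUCinf, which cannot be computed without lambda_z.

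**Working it through.** **Inputs.** Sampling times are from protocol 8.5.1. T1/2 of 12-13 h (adult), Tmax of about 1 h and the 40-50% share are from protocol 4.1.

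**1. Length of the window.** The last sample falls at 6/13 to 6/12 = 0.46-0.50 of a half-life. The 2-6 h regression window spans 4/13 to 4/12 = 0.31-0.33. Even if decline were purely terminal, concentration would fall by only 1 - 2^(-4/13) = 19% to 1 - 2^(-4/12) = 21% across that window.

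**2. Can one exponential reproduce the stated 40-50%?** With instant absorption, which maximises the early share:

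AUC0-6h/AUC0-24h = (1 - 2^(-6/T)) / (1 - 2^(-24/T))

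- T = 12 h: 0.2929/0.7500 = 39.1%
- T = 13 h: 0.2738/0.7219 = 37.9%

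With first-order absorption set to give Tmax 1 h, the values are 38.0% and 36.9%. The stated share is therefore not reached. Solving the formula for T gives 11.3 h at 40%, 8.5 h at 45% and 6.8 h at 50%. The shortfall at 12-13 h is 1-2 points at the 40% end (2-3 with Tmax 1 h) and 11-12 points at the 50% end (12-13 with Tmax 1 h). A share of 40-50% together with a 12-13 h terminal phase implies a faster early phase.

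**3. One worked profile.** The early-phase half-life and fast fraction are assumptions. Take

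C(t) = w·exp(-at) + (1-w)·exp(-bt) - exp(-ka·t)

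with terminal half-life 12.5 h (b = 0.0555), early half-life 2 h (a = 0.3466), w = 0.50 and ka = 3.00. This gives Tmax 1.0 h and a share of 45%, so it matches the protocol.

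- C(2) = 0.695, C(3) = 0.600, C(6) = 0.421
- Log-linear slope through these points: lambda_z = 0.1237, so T1/2 = 0.693/0.1237 = 5.6 h (0.45 of 12.5 h)
- Estimated AUCinf = AUC0-6h + C(6)/lambda_z = 3.48 + 3.40 = 6.88
- True AUCinf = w/a + (1-w)/b - 1/ka = 10.13
- CL/F is overstated by 10.13/6.88 = 1.47
- True share beyond 6 h: 1 - 3.48/10.13 = 66%; share that would be reported as extrapolated: 3.40/6.88 = 49%

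**4. Range over assumed profiles.** Terminal T1/2 is 12-13 h, Tmax 1 h, early-phase half-life 0.5-4 h, with no noise. The regression uses 1-2-3-6, 2-3-6 or 3-6 h.

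| AUC0-6h share | Apparent T1/2 | Fraction of true |
|---|---|---|
| 40% | 6.2-10.1 h | 0.48-0.84 |
| 45% | 4.3-7.2 h | 0.33-0.60 |
| 50% | 3.2-5.8 h | 0.25-0.49 |

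With the 2-3-6 h fit, CL/F is 1.10-1.80 times too high and Vz/F is 0.46-0.90 of the true value. A separate grid of bi-exponential profiles filtered on the same protocol figures gave T1/2 at 0.24-0.89 of true (median 0.51) and CL/F 1.07-1.86 times too high. T1/2 was low in every profile.

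**5. Extrapolated area.** Without any model, the protocol's projection leaves 50-60% of AUC0-24h after 6 h, so at least that share of AUCinf lies beyond the last sample. In the fits of step 4 it is 58-71%.

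**The case against.** Four points can be made for the plan.

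- **The parameters are peripheral.** Protocol 12.5.2 makes half-life optional, and both documents base the MF comparison on AUC0-6h and Cmax, neither of which is defined through lambda_z. Washout rests on adult data, and no section uses this trial's T1/2 for washout or dose selection. This stands. A reader might infer that the device comparison is compromised, but the documents do not support that.
- **The evidence for an early phase is thin at the lower end.** The share is a projection given as approximate, and 12-13 h is a rounded adult mean. At 40% the gap is 1-3 points, and a single half-life of 11.3 h would close it. Spread between subjects around the mean would also raise the average share a little. This stands as a limit on certainty at that end. It does not rescue the parameters, because step 1 alone shows a window of about a third of a half-life.
- **The size is not determined.** A reader might conclude that T1/2 would come out at about half its true value. That is a mid-range result of assumed profiles: it depends on where in 40-50% the share lies, on an early-phase rate found in neither document, and on the points regressed. No paediatric half-life is stated either.
- **Slopes might often fail to be estimable.** Simulating noisy single-exponential profiles can suggest failure in roughly half of periods, but that model conflicts with the protocol's 40-50%. No such rate is claimed here.

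**Conclusion.** The point holds as a fault in the descriptive PK parameters. The SAP and the protocol summary commit to terminal-phase quantities that samples to 6 h cannot supply, and they conflict with protocol 8.5.1 and 12.5.2.

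If the protocol's adult figures apply, T1/2 is biased low and CL/F high, and most of the true AUCinf lies beyond the last sample. The direction follows from the 40-50% share exceeding the 38-39% ceiling. The size does not follow from the documents: about 0.25-0.9 of the true value for T1/2 and 1.1-1.9 times for CL/F are illustrations under assumed bi-exponential, noise-free profiles with an adult terminal half-life.

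The primary estimates are unaffected by the bias itself. The only route to the primary analysis is the wording of the exclusion rule. Read literally, it could drop a patient whose AUCinf is missing in one period.

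**What to change.** 1. **SAP Table 2-1, and at the next amendment the protocol summary, Table 12-1 and the half-life sentence of 12.5.2:** remove AUCinf, lambda_z, T1/2, CL/F and Vz/F for MF. Cmax, Tmax and AUC0-6h then match protocol 8.5.1. AUClast is not listed there, so if it is kept, add it to that section.
2. **Alternative to removal:** report them only as apparent 0-6 h values, not as terminal or elimination parameters, under a stated lambda_z acceptance rule (minimum number of points, fit, maximum extrapolated share of AUCinf). The extrapolated share is computed from the fitted slope and so looks too small (49% against a true 66% in the worked profile). The label is therefore needed even when the rule is met.
3. **In the same edit, SAP 2.5.3 and protocol 12.4.3:** limit the exclusion rule to missing Cmax or AUC0-6h. Removing AUCinf from the tables alone would leave the rule citing a parameter that nobody derives.

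**Cost.** No change to patients, samples or the primary model. The SAP text can be revised directly. The protocol text needs a written amendment with the approvals set out in protocol 14.1. The trial would report no paediatric terminal half-life, but samples to 6 h could not have supplied one.

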#### 2.5.3 Handling of missing values/censoring/discontinuations

All drug concentrations below the lower limit of quantification (LLOQ) will be reported as "zero" and will be treated as zero for the calculation of PK parameters.

Patients with missing PK parameters (e.g. Cmax, AUClast, AUCinf) in one period will be excluded from the primary analysis.

Novartis	Confidential	Page 13 of 16
SAP Amendment 1		Study No. CQMF149G2203

In case a certain PK time point is not collected and missing in data, PK parameters may not be calculated from this treatment.

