# 2.5.1 **Primary endpoint**

The primary PK parameters of interest are Cmax, and AUC0-6h of MF after single dose administration of QMF149 75/40  $\mu$ g C1 and MF TH 100  $\mu$ g.

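### The primary-analysis exclusion rule names AUCinf, which the primary model does not use and 6-hour sampling may not support, so a child with valid Cmax and AUC0-6h could be excluded

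*SAP*

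**What the plan says.** SAP 2.5.1 sets the endpoints: "The primary PK parameters of interest are Cmax, and AUC0-6h of MF". SAP 2.5.2 fits the model to the same two: "Log-transformed PK parameters Cmax and AUC(0-6h) will be analyzed for mometasone furoate by linear fixed effects model". It has treatment and patient as fixed effects.

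The exclusion rule is in SAP 2.5.3, with the same wording in Protocol 12.4.3: "Patients with missing PK parameters (e.g. Cmax, AUClast, AUCinf) in one period will be excluded from the primary analysis". It removes the patient from the primary analysis as a whole, and AUC0-6h is not among its examples. The next sentence reads: "In case a certain PK time point is not collected and missing in data, PK parameters may not be calculated from this treatment".

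The documents differ on whether AUCinf is a routine MF parameter:

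- The Protocol summary lists it: "The following parameters will be calculated for MF AUC0-6h Cmax Tmax AUCinf".
- SAP 2.5.2 introduces its Table 2-1, which contains AUCinf, with "The following pharmacokinetic parameters (Table 2-1) will be determined using the actual recorded sampling times". Protocol Table 12-1 also lists it.
- Protocol 8.5.1 derives only Cmax, Tmax and AUC0-6h from the MF concentrations.
- Protocol 12.5.2 makes half-life optional, for qualitative use.

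Neither document states when a terminal slope or an AUCinf value is acceptable.

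**The concern.** With patient as a fixed effect, a child who lacks the modelled parameter in one period adds nothing to the treatment contrast. Excluding that child costs nothing. The rule loses information only when the missing parameter is one that the model does not use. AUClast comes from the same samples as AUC0-6h and would rarely be missing alone. AUCinf is different: it needs a terminal slope, and sampling covers only about half of one adult half-life.

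A child could therefore give every sample, have valid Cmax and AUC0-6h in both periods, and still be excluded because AUCinf could not be estimated. Protocol 9.1.1.1 defines completion by the two visits and all sampling time points, and replaces only dropouts and non-completers. This child is a completer. Unless more than 24 children complete, fewer than the planned 24 could be analysed, with some loss of precision.

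**Working it through.** **1. The plan's precision figure.** Protocol 12.8.1 and SAP 3 give 24 completers, an adult intra-patient CV of 30%, a 2-fold increase in variability, and limits of 72% to 138% with 90% coverage probability. Reading the increase as CV 60%, the log-scale SD is s = sqrt(ln(1 + 0.6²)) = 0.5545. At a true ratio of 1 the limits are exp(±h), with

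h = t(0.95, n−1) × s × sqrt(2/n) × sqrt(chi2(0.90, n−1)/(n−1)).

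At n = 24: h = 1.7139 × 0.5545 × 0.2887 × 1.1797 = 0.3236, giving 72.4% to 138.2%. The stated figure is reproduced.

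**2. Share of AUCinf beyond 6 h.** Protocol 4.1 projects AUC0-6h at 40-50% of AUC0-24h (f) and gives a half-life of 12-13 h. Taking AUC0-24h as 1 and an exponential tail with λ = ln 2 / half-life, the area beyond 6 h is (1 − f)/(1 − exp(−18λ)).

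- f = 0.40, 13 h: 0.60 becomes 0.972; share 0.972/(0.40 + 0.972) = 70.9%.
- f = 0.50, 12 h: 0.50 becomes 0.774; share 0.774/(0.50 + 0.774) = 60.7%.

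So about 61-71% is extrapolated. With Tmax near 1 h (Protocol 4.1) and MF samples at 0.5, 1, 2, 3 and 6 h (Protocol 8.5.1), three samples follow the peak.

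**3. How often the slope might fail.** This part rests on assumptions that are not in the documents:

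- Tmax is 1 h, with one decline rate k up to 6 h and a half-life of 12.5 h after that.
- k is chosen so that AUC0-6h/AUC0-24h is 40, 45 or 50%.
- The rise is either first-order absorption or linear to 1 h.
- Residual log SD is 5, 10, 15 or 20%.
- A period fails if a log-linear fit to 2, 3 and 6 h shows no decline.

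The sampling times have a sum of squares about their mean of 8.67, so p = Φ(−k × sqrt(8.67)/SD) per period. A child fails in at least one period with probability 1 − (1 − p)².

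| AUC0-6h / AUC0-24h | Rise | k per h | SD 5% | 10% | 15% | 20% |
|---|---|---|---|---|---|---|
| 40% | first-order | 0.0937 | 0 | 0.6 | 6.5 | 16.1 |
| 40% | linear | 0.1126 | 0 | 0.1 | 2.7 | 9.5 |
| 45% | first-order | 0.1627 | 0 | 0 | 0.1 | 1.7 |
| 45% | linear | 0.1793 | 0 | 0 | 0.0 | 0.8 |
| 50% | first-order | 0.2281 | 0 | 0 | 0 | 0.1 |
| 50% | linear | 0.2416 | 0 | 0 | 0 | 0.0 |

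Entries are % of children. Worked case (40%, first-order, SD 20%): p = Φ(−0.0937 × 2.944/0.20) = Φ(−1.379) = 8.38%, so 1 − 0.9162² = 16.1%. If missing in one period means exactly one, the loss is 2p(1 − p): 15.4% here, and 9.3% for the linear rise.

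**4. Effect on precision if exactly 24 complete.** 24 × (1 − 0.095) = 21.7 and 24 × (1 − 0.161) = 20.1 analysed. The formula in step 1 gives 71.1-140.7% at n = 22 and 69.6-143.7% at n = 20.

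**The case against.** The strongest reply is that the harmful reading is not the natural one. The list is marked as examples. The section deals with the primary objective, for which "PK parameters AUC0-6h and Cmax will be used for comparison of MF exposure after the two treatments". SAP 2.5 includes all patients evaluated for PK parameters. Protocol 8.5.1 does not derive AUCinf for MF at all, and the sentence after the rule concerns samples not collected. A sensible analyst might exclude a child only when the modelled parameter is missing. This stands: the text is ambiguous, and exclusion is possible rather than certain. It does not remove the point, because AUCinf is one of three named examples and is listed for calculation elsewhere.

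The second reply is that the failure rate cannot be known from the documents. That also stands. The highest figure needs the bottom of the 40-50% range, the largest assumed SD and one particular absorption shape.

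A reader might go further and infer that 6-hour sampling will remove a large part of the study. A single 12.5 h half-life from the peak onward does give much larger losses. But that curve, with first-order absorption, puts AUC0-6h at only 37.4% of AUC0-24h, outside the range in Protocol 4.1, so the documents do not support those losses.

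**Conclusion.** The rule names a parameter that the primary model does not use and omits one that it does. Applied as written, it could exclude a child with both primary parameters valid in both periods. The severity is minor. In the illustration the loss is at most about 2% at the 45-50% shapes. At the 40% shape with the largest SD it is about 9% to 15-16%. A stricter criterion for accepting the slope would raise these figures, and a steeper early decline would lower them, so they are not a bound. Even at 20 analysed, the limits widen only to about 70-144%.

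A reader might also infer that the primary comparison would be biased or that the stated precision is wrong. Neither follows. The stated precision is sound for 24 analysed. The illustration gives every child the same half-life, so it shows random loss only. No decision rule fails. The number analysed falls below 24 only if surplus completers among the roughly 32 recruited do not absorb the loss, and the interim analysis may change the target.

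**What to change.** Replace the sentence in SAP 2.5.3 and Protocol 12.4.3 with:

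> A patient is excluded from the analysis of a primary parameter (Cmax or AUC0-6h) only if that same parameter is missing in either period; missing AUClast, AUCinf, Lambda_z, T1/2, CL/F or Vz/F does not lead to exclusion.

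Report the extrapolated parameters descriptively, where they can be estimated. Bring Protocol 8.5.1 into line with the Protocol summary, Protocol 12.5.2 and SAP Table 2-1 on which MF parameters are derived.

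The cost is one sentence in each document and an aligned parameter list. No new data or analysis is needed, and a child who lacks a modelled parameter is treated as before.
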